Many other inflammatory cytokines/mediators have been implicated in the development of accelerated atherosclerosis and/or coronary plaque rupture⁹. For example, proinflammatory T-helper 1 (Th1) T cells are important macrophage activators and are the dominant T-cell type in atherosclerotic plaques²¹. T cells express GNRH receptors, and activation of these receptors via GNRH_a has been shown to stimulate T-cell expansion and differentiation into Th1 phenotype, suggesting that GNRH_a may promote destabilization of atherosclerotic plaques²² (Figure 2). Additionally, follicle-stimulating hormone (FSH) is upregulated following GNRH_a (e.g. leuprolide) but not GNRH-antagonists (e.g. relugolix), and has been implicated in excess adiposity, enhanced proinflammatory response secondary to adipocytes, and upregulation of RANK/osteoclast differentiation involved in calcium resorption (such as that found on stable coronary plaques)²³⁻²⁵. As such, the risk of atherosclerotic plaque destabilization and rupture may be mitigated with a GNRH-antagonist, such as relugolix.

[figure not shown]

Figure 2. Potential interaction between GNRH, immune effector response, and coronary atherosclerosis and plaque rupture resulting in major adverse cardiovascular events, such as myocardial infarction¹

An underlying factor that can contribute to the development of this increased CV risk are somatic mutations that impact immune frequency and function. In particular, somatic alterations associated with clonal hematopoiesis of indeterminate potential (CHIP) have been shown to lead to dysregulated inflammatory immune responses and poor CV outcomes¹². CHIP, present in 10-20% of the population over age 70, arises from somatic mutations in hematopoietic stem cells that produce abnormal circulating immune cells. These CHIP mutations are associated with twice the risk of CAD and ischemic stroke, as well as increased CV events^{11,26,27}. This is thought to occur via immune-mediated pathways, as CHIP-engineered mice have increased atherosclerosis mediated by inflammatory cytokines like IL-1 β , TNF α , and IL-6^{11,28,29}. However, how CHIP mutations impact CV outcomes following ADT in PCa men remains to be explored.

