Value of CCTA as Primary Endpoint: Coronary computed tomographic angiography (CCTA) has emerged as an accurate non-invasive method for the detection of obstructive coronary artery disease (CAD). Further, CCTA permits evaluation of numerous other coronary artery plaque characteristics, including plaque compositions, which are generally graded as non-calcified, calcified, and mixed⁴¹. Classification of plaques by CCTA based upon composition has important clinical implications: calcified plaque is generally considered more stable, while non-calcified or mixed plaques possess a thin cap fibroatheroma that is more likely to rupture and result in acute cardiac events such as a MI. Using CCTA, the evolution of these plaques after starting ADT will be evaluated in this study, providing mechanistic insight into the pathophysiology underlying GNRHa-mediated CV toxicity (i.e. immune- and FSH-mediated responses involving cytokines and biomarkers that will be studied in Aims 2 and 3). For example, if we observe an increase in coronary occlusion involving non-calcified lesions with GNRHa (but not relugolix), this finding would provide insight that GNRHa leads to downstream pathways involving plaque instability and rupture. If we also observe an increase in coronary occlusion involving calcified lesions with GNRHa (but not relugolix), this finding would provide insight that GNRHa may lead to FSH upregulation leading to osteoclast-mediated breakdown of calcified caps and plaque disruption. Thus, this imaging technique will both characterize and validate a novel imaging biomarker to predict men are at high risk of CV events after initiating ADT, as well as provide further validation of hypothesized mechanisms of GNRHa-mediated CV disease.

Aim 2: Determine the relationship between GNRH-agonist versus relugolix with downstream immune effector response that is implicated in atherosclerosis

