Analysis Plan: We will measure coronary plaque volume using CCTA images at both baseline and 12-months post-treatment initiation. The primary endpoint will be (1) total coronary plaque volume (continuous). Secondary endpoint will be non-calcified coronary plaque volume (continuous). Other outcome measures include (1) calcified plaque volume (continuous), (2) low-attenuation plaque volume (continuous), (3) coronary artery calcification score (continuous), and (4) coronary vessel stenosis (ordinal). The change in endpoint metrics between baseline and 12-month will be estimated for leuprolide versus relugolix versus no ADT. Data transformation to fit statistical assumptions will be done as needed. In addition, we will implement multivariable models that control for potential confounders (e.g. age, statin medication use) using general linear regression and/or logistic regression.

Power: We hypothesized that there will be significantly greater total plaque burden (i.e. summation of total plaque volume of all major coronary territories) increase from baseline to month 12 following GNRHa versus no ADT or relugolix. Using a standard deviation of 30 mm³ for the change in total plaque volume from scans obtained at two time points approximately 12 months apart in the study, 60 participants (30 in each comparative treatment arm) with both baseline and month 12 CCTA would provide 80% power to detect a difference of ≥ 20 mm³ in the change in total plaque volume [$P(X>Y) 0.72$] from baseline to 12 months.

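### Plaque-type imaging, as planned, cannot tell an instability effect of GNRHa from general, proportional acceleration of all plaque

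*Combined protocol and SAP*

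**What the plan says.** Section 4, Aim 1 (Value of CCTA as Primary Endpoint) attaches a mechanism to each plaque type. For the first, it says that "an increase in coronary occlusion involving non-calcified lesions with GNRHa (but not relugolix), this finding would provide insight that GNRHa leads to downstream pathways" of instability and rupture. The second is introduced as an addition: "If we also observe an increase in coronary occlusion involving calcified lesions with GNRHa (but not relugolix"), which it takes to suggest FSH upregulation and osteoclast breakdown of calcified caps. It concludes that the imaging will "provide further validation of hypothesized mechanisms of GNRHa-mediated CV disease".

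The Analysis Plan for Aim 1.1 in Section 6 ranks the outcomes. At the top stands the overall volume: "The primary endpoint will be (1) total coronary plaque volume (continuous"). One step down, the first measure that carries plaque type appears: "Secondary endpoint will be non-calcified coronary plaque volume (continuous"). The lowest tier takes in the rest: "Other outcome measures include (1) calcified plaque volume (continuous), (2) low-attenuation plaque volume (continuous), (3) coronary artery calcification score (continuous"), and then ordinal stenosis. Each is a separate outcome compared between groups. No share, ratio or other measure of relative composition is planned. The Power paragraph describes total plaque as a "summation of total plaque volume of all major coronary territories".

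The text on Aim 2 in Section 4 says that Aim 1 tests two explanations, separately or together: faster atherosclerosis and less stable plaque.

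On the FSH pathway, Section 3 describes "upregulation of RANK/osteoclast differentiation involved in calcium resorption (such as that found on stable coronary plaques").

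**The concern.** The primary objective in Section 1 is mechanistic and is to be studied with imaging as well as blood biomarkers. For the imaging part to say which explanation applies, it needs a result that one explanation predicts and the other does not.

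A greater rise in non-calcified volume under GNRHa is not such a result. It is expected if GNRHa favours unstable plaque. It is equally expected if GNRHa multiplies all plaque by the same factor, because the non-calcified part then grows with the rest. Under Section 4 the second case could be reported as validation of an instability pathway. Perfect control of type I error would not help, because the test answers a different question.

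The calcified reading has a further gap. Section 3 describes calcium being resorbed, while Section 4 takes an increase involving calcified lesions as support. The direction that the FSH pathway predicts for calcified volume is never stated, so a rise or a fall could be claimed afterwards.

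**Working it through.** **The plan's own figure.** The Power paragraph gives a difference of 20 mm³, SD 30 mm³, 30 per arm and 80% power. The standard error is 30 × √(2/30) = 7.746 mm³, and 20/7.746 = 2.582.
- Two-sided 5%: Φ(2.582 − 1.960) = 73.3% (71.9% with the t distribution).
- One-sided 5%: Φ(2.582 − 1.645) = 82.6% (81.8% with the t distribution).

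So the stated 80% is approached only one-sided; sidedness is not given. The stated P(X>Y) of 0.72 is also not what 20/30 implies under normality: Φ(20/(30√2)) = 0.681. Neither matter drives this point. Two-sided 5% is used below.

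**Model with no composition effect.** Let f be the non-calcified share. The excess of 20 mm³ under GNRHa is split 20f to non-calcified and 20(1 − f) to calcified. Component SDs are in the same proportion, scaled so that the total has SD 30. Assumed, because the documents do not give them: f from 50% to 80%, correlation ρ between component changes from 0 to 0.9, and total equal to the two components, with mixed plaque counted as non-calcified.

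**One setting by hand (f = 0.7, ρ = 0).**
- Scale: 30/√(0.7² + 0.3²) = 39.4, so the SDs are 27.6 (non-calcified) and 11.8 (calcified).
- Non-calcified difference: 0.7 × 20 = 14; standard error 27.6 × 0.2582 = 7.12; ratio 1.97; power about 50%.
- Non-calcified volume is thus significant in about half of all trials with no composition effect present.

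**Simulation over the grid, given a positive primary (20,000 trials per setting).**

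| Event under purely proportional growth | Share of positive trials |
|---|---|
| Non-calcified volume significantly higher | about 56–97% |
| At least one component significantly higher | about 87–99.9% |
| Relative contrast (1 − f) × non-calcified − f × calcified significant | about 5% |

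The last row is a linear stand-in for a log-ratio test. Its mean under proportional growth is zero: for f = 0.7, 0.3 × 14 − 0.7 × 6 = 0. The log ratio has the same property, because a common growth factor cancels from numerator and denominator.

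**Relugolix condition read within arm.** Suppose the reading requires a significant rise under GNRHa and none under relugolix. Given a positive primary, at least one component meets this in 97–99.5% of trials with no background growth under relugolix, 78–98% with 10 mm³, and 12–61% with 20 mm³ (share 50–85%). For non-calcified volume alone the frequency cannot be higher.

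**Why the scale matters.** An arm-by-component test on raw mm³ compares 20f with 20(1 − f), a gap of 20(2f − 1). Under proportional growth this is 0 only at f = 0.5. It is 6 mm³ at f = 0.65 and 12 mm³ at f = 0.8. Such a test falsely flags composition in roughly 12–66% of trials at shares of 65–80%.

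**Power of the relative contrast (linear stand-in).** At f = 0.7 and ρ = 0 its SD is √((0.3 × 27.6)² + (0.7 × 11.8)²) = 11.7 and its standard error 3.02. If all 20 mm³ were non-calcified, the contrast is 0.3 × 20 = 6 and power is 51%. If all were calcified, it is 0.7 × 20 = 14 and power is above 99%. Over shares of 50–85% and correlations of 0–0.6 the ranges are about 46–99.9% and 73–100%. The log-ratio contrast itself was not simulated, because the documents give no baseline component volumes.

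**The case against.** The strongest reply is that Section 4 is illustrative rationale, not a decision rule. A reader might infer something harsher: that the primary is the sum of the two components, so any positive primary yields a mechanism by construction. The documents do not support that.
- Section 4 speaks of occlusion involving a lesion type, not component volume. Stenosis is a separate ordinal outcome, and volumes that add up do not force stenosis to rise.
- Total plaque is described as a sum over territories. That it also equals the sum of types is an inference, and Section 6 lists a mixed class that is not allocated.
- The calcified reading is an addition to the non-calcified one, so growth in either component is not the stated rule. The non-calcified row of the table is the relevant one.
- The condition on relugolix excludes similar growth in both arms. It is therefore too strong to say that nothing could count against the readings.

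Two further points stand. Accelerated atherosclerosis under GNRHa is itself part of the hypothesis in Section 2, so proportional growth would not refute the trial's idea. Aims 2 and 3 also bring immune, proteomic and genomic evidence on mechanism.

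These replies limit the point without removing it. The Aim 1 outcomes with plaque type attached are absolute volumes, the stenosis outcome is not tied to plaque type, and stenosis by lesion type could also rise under general acceleration. No planned imaging analysis separates the two limbs, yet the word used is validation.

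**Conclusion.** The point holds in limited form. Composition as planned cannot distinguish plaque instability from general acceleration of atherosclerosis. On the plan's figures, purely proportional growth makes non-calcified volume significant in about 56–97% of trials with a positive primary, against about 5% for a contrast on relative composition. These figures rest on the assumed shares, correlations and proportional SDs. They also take the readings as between-arm comparisons of volume. A within-arm reading of the relugolix condition can bring the frequency well down if relugolix patients have appreciable background growth.

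The primary comparison is unaffected. What is affected is the claim that imaging by plaque type validates a particular mechanism.

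**What to change.** 1. Add one prespecified secondary contrast to the Aim 1 Analysis Plan: the GNRHa-minus-relugolix difference in 12-month change of log((non-calcified + mixed)/calcified volume), adjusted for the baseline log ratio. State a rule for zero volumes, for example a small offset with a sensitivity analysis, and report how many men contribute.
2. If a bivariate arm-by-component model is used instead, fit it on the log or proportional scale, not in raw mm³.
3. Reword Section 4. A shift towards non-calcified plaque is consistent with instability. No detected shift means that imaging has not identified a composition-specific mechanism; it neither proves proportional acceleration nor counts against accelerated atherosclerosis.
4. State the sign that the FSH pathway predicts for calcified volume, and reconcile Sections 3 and 4 on it.
5. Keep the component volumes as planned outcomes.

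The cost is wording and one analysis of data already collected. Mechanism claims from imaging become harder to make, power for the contrast may be modest, and men without measurable plaque add little to it.

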1. Study Summary

Project Title	Biomarker-Based Approaches to Understand and Predict Cardiovascular Toxicity from Androgen Deprivation Therapy Targeting the Gonadotropin Releasing Hormone Pathway in Prostate Cancer Men
Project Design	Open-label randomized clinical trial with parallel prospective cohort study
Primary Objective	Elucidating the pathophysiologic link between gonadotropin releasing hormone agonist hormone therapy (e.g. Lupron) and cardiovascular (CV) toxicity, and the mechanism by which CV risk-reduction is achieved by the novel oral GNRH-antagonist, relugolix. This objective will be studied using imaging and blood biomarkers.
Secondary Objective(s)	Identify genomic alterations that predispose an individual to enhanced CV toxicity following hormone therapy with GNRHa or relugolix
Research Intervention(s)/Interactions	A) GNRHa versus relugolix [randomization] B) Parallel, non-interventional cohort of men receiving no hormone therapy
Study Population	Men >18 years with localized intact or recurrence prostate cancer undergoing radiation therapy (with or without prior prostatectomy), with or without hormone therapy
Sample Size	90 men (30 men in GNRHa arm, 30 men in relugolix arm, 30 men in non-hormone therapy cohort)
Study Duration for individual participants	12 months
Study Specific Abbreviations/Definitions	Radiation therapy (RT) Androgen deprivation therapy (ADT) Gonadotropin-releasing hormone agonist (GNRHa) Gonadotropin-releasing hormone antagonist (GNRHaa) Nonsteroidal anti-androgen (AA) Combined androgen blockade (CAB) Major adverse cardiac events (MACE)
Funding Source (if any)	Prostate Cancer Foundation-Pfizer-Myovant Challenge Award, Prostate Cancer Foundation Young Investigator Award

2. Objectives

Androgen deprivation therapy (ADT) with a gonadotropin-releasing hormone agonist (GNRHa) is a highly effective and commonly used treatment for prostate cancer (PCa) with over 500,000 men with PCa receiving ADT annually in the United States^{3,4}. However, large observational studies suggest GNRHa is associated with increased risk of myocardial infarction (MI) and sudden cardiac death, raising concerns that ADT causes cardiovascular (CV) harm⁴⁻⁶. In fact, as more men survive PCa due to increasing ADT use, **CV**

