To examine the role that the immune system plays in ADT-induced CV disease, we propose a mixed-methods clinical study using patient-level data from our Cardio-Oncology PROstate Cancer (CO-PRO) institutional, open-label prospective clinical trial. In this study, patients with stage I-III PCa will receive leuprolide or relugolix with radiation therapy, or radiation alone. Using imaging and peripheral blood samples from this trial, ***the main goal of this proposal is elucidating the pathophysiologic link between GNRHa and CV toxicity and the mechanism by which CV risk-reduction is achieved by the novel oral GNRH-antagonist, relugolix***. We hypothesize that ***early CV toxicity from GNRHa is mediated by a GNRHa-activated inflammatory cascade directly impacting vascular integrity and resulting in accelerated coronary atherosclerosis, and this effect will not be observed in men receiving relugolix***. Aim 1 of this study will utilize non-invasive imaging to identify how leuprolide versus relugolix affect the development of coronary artery disease, and whether validated imaging biomarkers can predict these changes. As secondary laboratory-based correlative studies, Aim 2 will evaluate how pre-existing or augmented immune responses following ADT predict for development of CV toxicity. Finally, in Aim 3 we will examine how pre-existing genomic alterations that pre-dispose an individual to enhanced inflammatory immunity (and have been associated with accelerated atherosclerosis) correlate with the development of CV toxicity following ADT with leuprolide or relugolix. By identifying major contributors to CV risk from ADT, we will ultimately develop a precision medicine approach to optimize risk prediction and allow clinicians to appropriately counsel patients on risk-benefit ratio of ADT and utilize novel risk-reducing ADT agents such as relugolix.

3. Background

Association of ADT and Cardiovascular Morbidity

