The role of ADT in CV harm was ignited with the publication of large observational studies in the past decade, which suggested that ADT use in the form of a GNRHa for PCa men was associated with a 20% increased risk of CAD, 10-30% increased risk of MI, and a 15% increased risk of sudden cardiac death⁴⁻⁶. With increasing ADT use and improving radiation/surgical technique, ***CV mortality, not cancer, is now the most common cause of death in PCa patients***^{7,8}. Additionally, while the addition of ADT with radiation therapy has been shown to improve survival for men with unfavorable risk PCa, multiple post-hoc studies have suggested that the addition of ADT may result in a survival *detriment* in men with CV comorbidities^{13,14}.

Traditionally, CV injury following ADT is thought to be driven by an indirect mechanism of prolonged hypogonadism precipitating metabolic syndrome, insulin resistance, and weight gain over several years^{7,15-17}. However, the effect of ADT, namely GNRHa, may be direct. There are several observations from recent studies that support this premise. First, studies have shown that ADT, after only 3-6 months of therapy, is associated with an increased risk of atherothrombotic events^{7,8}. Second, data from the recent HERO trial² evaluating GNRHa (leuprolide) versus GNRH-antagonist (relugolix) in PCa men showed an increased incidence of major adverse CV events with GNRHa compared with GNRH-antagonist as soon as 4 weeks after initiation of treatment (Figure 1). Further, testosterone suppression was greater with GNRH-antagonist than GNRHa, countering the testosterone-mediated CV effect. Finally, the excess CV event risk with ADT in the large observational studies mentioned above⁴⁻⁶ was seen with GNRHa therapy, not orchiectomy/surgical castration. In fact, meta-analysis of several observational studies⁵ have shown a hazard ratio for risk of MI with GNRHa (compared with other forms of ADT) to be 1.57 (95% CI 1.26-1.94). Nonetheless, GNRHa remains the most widely utilized form of ADT in the United States due to lower cost, convenience in delivery, and minimal injection-associated adverse effects compared with injectable GNRH-antagonist.

[figure not shown]

Figure 1. Incidence of major adverse cardiac events (MACE) in men with advanced PCa receiving leuprolide versus relugolix. Incidence curves separate immediately after onset of treatment, with GNRHa resulting in more MACE².

Association of Immune Response and Coronary Atherosclerosis

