Aim 2.1: To determine how pre-existing and ADT-augmented inflammatory immune responses impact CV toxicity, we will evaluate pre-treatment, 3-, 6-, and 12-month peripheral blood mononuclear cells (PBMC) samples from all patients enrolled on trial. We will first evaluate the frequency and function of inflammatory immune populations by flow cytometry. While we will include a comprehensive panel evaluating lymphocyte and myeloid populations, we will specifically conduct an in-depth analysis quantifying the frequency, phenotype, and activation of T cells and macrophages. In particular, we will evaluate the frequency of naïve (CD44-CD62L+), effector memory (CD62L^{lo}CCR7-CD27^{lo/int}), central memory (CD62L^{hi} CCR7^{hi} CD44^{hi}), CD4 T-helper subsets (staining for the transcription factors Tbet, EOMES, ROR γ , and GATA), and CD4+ Tregs cells (CD25+GITR+CD127-Foxp3+)⁴⁷. Circulating macrophages will be evaluated for inflammatory M1 (CD80, CD86) and immunosuppressive M2 (CD163, CD206) sub-populations. Immune cells will also be evaluated for expression of GNRH receptors, as well as function by expression of intracellular cytokines associated with T cell activity (including IFNy, TNF α , IL-2, IL-4, IL-6, IL-10, and Granzyme B as we have published^{48,49}) or macrophage activity (Arg1, TNF σ , IL-6, IL-12).

Protocol Title: Mechanism and Predictors of Cardiotoxicity after Prostate Cancer Treatment: A Parallel Cohort and Randomized Trial Comparing Radiation Alone, Radiation plus Leuprolide, and Radiation plus Relugolix

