In addition to evaluating peripheral immune populations, plasma will be isolated at the same timepoints and evaluated for chemokine and cytokine production by multiplex assay (Human Cytokine/Chemokine/Growth Factor 71-Plex Clinical Assay, Eve Technologies). This assay measures both inflammatory and suppressive chemokines and cytokines, as well as growth factors involved in cardiac activity. Factors found to be altered via multiplex (either following ADT, between treatment groups, or between patients who develop CV toxicity) will be validated by ELISA. Finally, to evaluate the mechanistic significance of these alterations, human cardiac myocytes (the AC16 cell line and primary cardiomyocytes (Sigma Aldrich)) grown under wild-type or androgen-deprived conditions will be evaluated for altered expression of these factors by ELISA. Supernatants from these cells will be used in transwell migration assays to evaluate how androgen deprivation-induced alteration of these factors impacts the migration of T cells, macrophage, or other relevant immune populations across a transwell. Follow-up experiments will be conducted in which altered factors are either blocked or restored (recombinant protein) to determine if these factors are sufficient to alter immune migration towards cardiac cells.

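### Section 4 says FSH-mediated responses will be studied through Aims 2 and 3, but no FSH assay or analysis is listed, so that branch of the mechanism cannot be confirmed or refuted as planned

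*Combined protocol and SAP*

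**What the plan says.** Section 1 sets the primary objective as the mechanism of GNRHa cardiovascular toxicity and of the lower risk with relugolix: "This objective will be studied using imaging and blood biomarkers". Section 2 gives the main hypothesis as inflammatory: "early CV toxicity from GNRHa is mediated by a GNRHa-activated inflammatory cascade directly impacting vascular integrity".

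Section 3 (immune response and coronary atherosclerosis) adds a second route. Citing published work, it says that "follicle-stimulating hormone (FSH) is upregulated following GNRH_a (e.g. leuprolide) but not GNRH-antagonists (e.g. relugolix"), and it links FSH to adiposity, to a proinflammatory response and to osteoclast differentiation.

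Section 4, on the value of CCTA, then says the imaging will give insight into "immune- and FSH-mediated responses involving cytokines and biomarkers that will be studied in Aims 2 and 3". It assigns a reading to each lesion type. More occlusion involving non-calcified lesions points to plaque instability. For more occlusion involving calcified lesions, "this finding would provide insight that GNRHa may lead to FSH upregulation leading to osteoclast-mediated breakdown of calcified caps and plaque disruption".

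Section 6, Aim 2.1, starts with cells: "We will first evaluate the frequency and function of inflammatory immune populations by flow cytometry". Plasma from the same four time points is to be "evaluated for chemokine and cytokine production by multiplex assay (Human Cytokine/Chemokine/Growth Factor 71-Plex Clinical Assay, Eve Technologies"). Aim 2.2 is PBMC proteomics and Aim 3 is exome sequencing of pre-treatment PBMC.

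**The concern.** FSH appears in the current plan as background (section 3) and as an interpretation of CT findings (section 4). It does not appear as a measured variable. If the calcified-lesion pattern is seen, the plan invites a statement about a hormone for which the trial would hold no value.

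The gap also touches how the inflammatory results are read. Because section 3 ties FSH to a proinflammatory response, a higher inflammatory signal in the GNRHa arm could, on the protocol's own account, come partly from FSH. Aim 2 could detect that signal but could not say whether FSH moved with it.

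At stake is one branch of the mechanistic conclusion, not the comparison of plaque volume between arms.

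**Working it through.** There is no stated figure to reproduce. The check is whether anything listed for Aims 2 and 3 could supply the FSH evidence that section 4 refers to.

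**Step 1: assays listed in section 6.**

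| Assay | Material | Timing | Names FSH? |
|---|---|---|---|
| Flow cytometry (Aim 2.1) | PBMC | Baseline, 3, 6, 12 months | No |
| 71-plex panel, ELISA follow-up (Aim 2.1) | Plasma | Baseline, 3, 6, 12 months | No; analytes not itemised |
| Mass-spectrometry proteomics (Aim 2.2) | PBMC | Baseline, 12 months | No |
| Exome sequencing (Aim 3) | PBMC | Baseline | No |

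Four families are listed and none names FSH. Nor does any name testosterone or an osteoclast or RANK marker. The ELISA step covers only factors that the multiplex finds altered, so it cannot bring in a hormone that is not on the panel. Proteomics is run on lysed cells, which does not give a circulating hormone level. Exome sequencing of a pre-treatment sample cannot show what FSH does on treatment.

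**Step 2: analyses.** The Aim 2 plan compares marker change between treatment groups by Kruskal-Wallis test, links percentage change to the Aim 1 metrics, and applies Holm-Bonferroni. The Aim 3 plan uses Spearman correlations and the same linking approach. Neither mentions FSH.

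**Step 3: the two routes side by side.** The T-cell route has direct measurements: T-cell subsets, intracellular cytokines and GNRH receptor expression. The FSH route has only calcified-lesion findings on CT and inflammatory cytokines, and neither is specific to FSH.

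**Step 4: samples available.** Section 1 gives 30 men per group, and section 7 gives four draws with plasma kept.
- Randomised arms: (30 + 30) x 4 = 240 samples.
- With the no-ADT cohort: 90 x 4 = 360 samples.

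Both are upper limits that assume every draw is obtained.

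**Step 5: multiplicity cost.** Assume the Holm-Bonferroni family is the 71 plasma analytes with one test each. Adding FSH tightens the strictest threshold by 1 - 71/72 = 1.4%. Adding FSH and testosterone tightens it by 1 - 71/73 = 2.7%. A larger family makes either change smaller.

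**The case against.** The strongest reply is that section 4 is being read too literally. What will be studied, on one natural reading, is the cytokines and biomarkers, with FSH only describing the process behind them. The calcified-lesion sentence is hedged and offered as an example. No objective, hypothesis or endpoint names FSH. All of that is fair, and it limits the point. It does not remove it, because on either reading the listed cytokines cannot distinguish an FSH effect from another inflammatory source.

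A second reply is that absence is not proven. The 71-plex analytes and the routine laboratory data are not itemised, and the Schedule of Events mentioned in section 14 is not in the text available. This stands: an FSH assay is not listed, but it cannot be said that FSH will not be measured. Even if it were drawn routinely, no stated analysis relates it to plaque.

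A third reply is that adding FSH would not prove mediation. It would mainly check a drug effect that section 3 already cites, and with 30 men per arm its link to plaque is only an association. This also stands, and the fix is worded accordingly.

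A reader might also infer that CT cannot separate the two routes because both lesion patterns are counted against GNRHa. The text does not support that: section 4 reads the two lesion types differently, and section 6 analyses calcified and non-calcified volume separately. The sound point is only that lesion type does not measure FSH.

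**Conclusion.** The point holds in a limited form. Section 4 presents FSH-mediated responses as studied and reads a CT pattern as insight into FSH upregulation, yet none of the four listed assay families and neither analysis plan names FSH. The FSH branch can therefore be neither confirmed nor refuted as planned. This rests on the assays named in the text and on calcified change not being specific to FSH.

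A reader might infer that the whole mechanism objective cannot be answered. The documents do not support that: the objective is framed around imaging and blood biomarkers generally, and the inflammatory hypothesis in section 2 has both assays and analyses.

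A reader might also infer that the lack of a testosterone assay contradicts the plan. It does not, because testosterone is never promised. Section 3 addresses the hypogonadism explanation from a published trial, where "testosterone suppression was greater with GNRH-antagonist than GNRHa, countering the testosterone-mediated CV effect". Section 6 allows ADT of 6 to 24 months, so some men may be off treatment at the 12-month scan. That the arms would then differ in hormone recovery is conjecture. Testosterone is at most an optional addition.

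The change is worth making because it is small and lets the trial check a step that it says it will study.

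**What to change.** In section 6, Aim 2.1, add FSH measured on the plasma already isolated at baseline, 3, 6 and 12 months. In the Aim 2 analysis plan, compare FSH between the two randomised arms and include it among the markers related to 12-month plaque change. State that this is reported as association and not as proof of mediation.

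Total testosterone on the same samples is optional. It would describe the rival hypogonadism route raised in section 3.

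The cost is the assays themselves, some plasma volume, and one or two more tests in the Holm-Bonferroni family. The documents give neither an assay price nor the residual volume. Section 7 specifies EDTA tubes, so the laboratory should confirm that stored EDTA plasma suits the assay. No new visit or draw is needed.

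If FSH is not to be measured, a wording change is enough. Reword section 4 so that plaque composition is not read as evidence of FSH upregulation, and remove FSH-mediated responses from what Aims 2 and 3 are said to study.
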